### 4.6 Analysis Sets

For purposes of analysis within this SAP, the following populations are defined:

**Full Analysis Set (FAS):** All patients who are randomized and received any amount of Study Drug (olezarsen or placebo). The FAS represents the practically feasible intent-to-treat (ITT) population as delineated in International Conference on Harmonization (ICH) Guideline E9. This set will be used for the primary analysis of efficacy.

**Per Protocol Set (PPS):** Subset of the FAS who received at least 5 monthly doses of Study Drug within the first 6 months of the Treatment Period, have a baseline fasting TG assessment, and who have no significant protocol deviations that could compromise the interpretation of efficacy. Significant protocol deviations will be determined prior to unblinding for statistical analysis. This set will be used for supportive inferences concerning efficacy.

**Safety Set:** All patients who are randomized and received any amount of Study Drug. This set will be used for all safety analyses.

**PK Set:** All patients who are randomized and received any amount of olezarsen and have at least 1 evaluable concentration result post-first dose. This set will be used for analysis of PK data.

The number and percentage of subjects in each analysis set will be summarized by treatment group, total olezarsen treated, and overall based on randomized patients.

A by-subject listing of analysis sets, including the inclusion/exclusion flag for each analysis set and reasons for exclusion from each analysis set, will be provided.

## 4.7 Medical History

The medical history will be coded to System Organ Class (SOC) and Preferred Term (PT) using the Medical Dictionary for Regulatory Activities (MedDRA). The final MedDRA version used will be designated in the clinical study report. The number and percentage of subjects reporting a medical history will be summarized by SOC, PT and by treatment group, total olezarsen treated, and overall, using the Safety Set.

A by-subject listing of medical history will be provided.

A separate table will be created for the targeted medical history based on the Safety Set. The number and percentage of patients with below targeted medical history terms will be summarized accordingly. A listing of targeted medical history will be provided.

### **Cardiac-related history:**

- Atherosclerotic CV disease [ASCVD]
  - Coronary artery disease [CAD]
    - Angiographic evidence of  $\geq 50\%$  Stenosis in 1 or more major epicardial coronary arteries
    - Cardiac Ischemia on exercise stress test/imaging
    - Coronary Artery calcium scan completed with a score  $>100$
    - Myocardial Infarction (MI)
    - Percutaneous coronary intervention [PCI]
    - CABG
  - Cerebrovascular Disease
    - Ischemic Stroke
    - Carotid Artery Disease defined by the ASCVD criterion
      - $\geq 50\%$  carotid artery stenosis
      - Carotid Endarterectomy
      - Carotid artery revascularization(s) other than Carotid Endarterectomy (either surgical or stenting)
  - Peripheral artery disease
    - Peripheral Revascularization
    - Aorto-iliac Revascularization
    - Lower extremity amputations due to Peripheral Artery Disease
    - Ankle-brachial index  $< 0.9$  with symptoms of intermittent claudication
    - Ankle-brachial index  $< 0.9$  without symptoms of intermittent claudication

- TIA
- Any Stroke
- Hemorrhagic Stroke
- Other Cerebrovascular disease
- Unstable Angina
- Heart failure
- Current NYHA Class
- Atrial fibrillation

**Other risk factors:**

- Diabetes mellitus Type 1
  - Duration (in years) of diabetes mellitus Type 1, duration being calculated as the year of informed consent from (ICF) minus the start year of the disease plus one.
- Diabetes mellitus Type 2
  - Duration (in years) of diabetes mellitus Type 1, duration being calculated as the year of ICF minus the start year of the disease plus one.
- Hypertension requiring pharmacologic treatment
- Smoking
  - Current
  - Former
- Chronic kidney disease
  - stage

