## 5.2 Exclusion Criteria

1. Diabetes with any of the following:
  - a. Newly diagnosed within 12 weeks of screening
  - b. HbA1c  $\geq 9.5\%$  at Screening
  - c. Change in basal insulin regimen  $> 20\%$  within 3 months prior to Screening
  - d. For patients with type 1 diabetes: episode of diabetic ketoacidosis, or  $\geq 3$  episodes of severe hypoglycemia within 6 months prior to Screening
2. Acute coronary syndrome or stroke/TIA within 6 months prior to Screening
3. Major surgery, peripheral revascularization, or non-urgent percutaneous coronary intervention (PCI) within 3 months prior to Screening, or upcoming planned major surgery or major procedure (e.g., arterial revascularization) during the course of the study
4. Active pancreatitis within 4 weeks prior to Screening
5. Screening laboratory results as follows, or any other clinically significant abnormalities in screening laboratory values that would render a patient unsuitable for inclusion:
  - a. Alanine aminotransferase (ALT) or aspartate aminotransferase (AST)  $> 3.0 \times \text{ULN}$
  - b. Total bilirubin  $> 1.5 \text{ ULN}$  unless due to Gilbert's syndrome
  - c. Estimated GFR (eGFR)  $< 30 \text{ mL/min/1.73 m}^2$  [as determined by the CKD-EPI formula for creatinine clearance; (Levey et al. 2009)]
  - d. Urine protein/creatinine ratio (UPCR)  $\geq 500 \text{ mg/g}$
6. Uncontrolled arterial hypertension (BP  $> 180/100 \text{ mmHg}$ ) despite antihypertensive therapy
7. Uncontrolled hypothyroidism such as those with thyroid stimulating hormone (TSH)  $> 1.5 \times \text{ULN}$  and free thyroxine (T4)  $< \text{LLN}$ , clinical evidence of hypothyroidism, or thyroid hormone therapy that has not been stable for  $\geq 4$  weeks prior to Screening
8. Active infection requiring systemic antiviral or antimicrobial therapy that will not be completed prior to Study Day 1 or active Covid-19 infection with or without therapy that will not be resolved by Study Day 1
9. Active infection with human immunodeficiency virus (HIV), hepatitis C or hepatitis B (e.g., HBsAg positive) diagnosed by initial serological testing and confirmed with RNA testing, or prior treatment for hepatitis C. Patients at Screening who test positive by serology (for example, positive for Hepatitis C antibody), but negative by RNA may be allowed in consultation with the Sponsor Medical Monitor or designee

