#### 4.9.1.7 Examination of Subgroups

Subgroup analyses of the primary efficacy and applicable secondary endpoints will be made to assess consistency of analysis results over subgroups. The subgroups include but are not limited to:

- Baseline fasting TG  $\geq$  500 mg/dL vs. < 500 mg/dL
- Baseline fasting TG  $\geq$  200 mg/dL vs. < 200 mg/dL
- age groups (< 65,  $\geq$  65 years)
- race (White vs non-White)
- Sex (male, female)
- ethnicity (Hispanic or Latino vs. Not Hispanic or Latino)

- Baseline BMI (< 25, 25 to < 30, 30 to < 40, ≥ 40 kg/m^2)
- diabetic status (diabetic vs non-diabetic)
- Baseline Hemoglobin A1C (HbA1c): < 6.5 vs. ≥ 6.5
- Baseline background therapies (lipid-modifying therapy versus none; statins versus no statins; Fibrates vs. no Fibrates)
- Previous treatment with volanesorsen: Yes vs. No

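### SAP 4.7 adds a whole year to diabetes duration, overstating it by up to 2 years, and the Type 2 duration line is labelled Type 1

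*Combined protocol and SAP*

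**What the plan says.** SAP section 4.7 sets out a targeted medical history summary: "A separate table will be created for the targeted medical history based on the Safety Set". A listing accompanies it. Under its list of other risk factors, each diabetes type has a sub-bullet for duration in years.

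- Under Type 1 the rule is "duration being calculated as the year of informed consent from (ICF) minus the start year of the disease plus one".
- Under the bullet "Diabetes mellitus Type 2" the sub-bullet is again headed "Duration (in years) of diabetes mellitus Type 1", with the same rule: "duration being calculated as the year of ICF minus the start year of the disease plus one".

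The SAP gives no reason for the added year and no separate definition of Type 2 duration. Protocol section 5.2, criterion 1a, excludes diabetes that was "Newly diagnosed within 12 weeks of screening", so durations of little more than 12 weeks are permitted.

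**The concern.** Adding one is correct when days are counted inclusively, because the first and last day both count. The SAP does this in section 4.2.1, where time at risk is a difference between dates plus one day, divided by 365.25. That adds 1/365.25, or about 0.003 year. Section 4.7 adds one to a difference of calendar years, which adds a full year. The result is a count of the calendar years touched, but it is labelled a duration in years.

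The error has one sign, so averaging over patients does not remove it. It is proportionately largest in recently diagnosed patients. The second problem is separate: read literally, the line under Type 2 asks for the duration of Type 1 disease. What is at stake is the accuracy of one descriptive row per diabetes type.

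**Working it through.** The documents give no numerical diabetes duration, so there is no figure to reproduce. The check is on the rule itself.

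**Inputs.** The rule is consent year minus start year plus one (SAP 4.7). The minimum duration at Screening is about 12 weeks (protocol 5.2). The distribution of consent and onset dates is not given and is assumed below.

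**Algebra.** Write consent as Y1 + u and onset as Y0 + v, where u and v are the fractions of the calendar year elapsed, each at least 0 and below 1.

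- True duration = Y1 − Y0 + u − v
- SAP value = Y1 − Y0 + 1
- Overstatement = 1 − u + v, which is above 0 and below 2
- Mean overstatement = 1 + E[v] − E[u]

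**Range.** All 365 × 366 day pairs with consent in 2022 and onset in 2012 give a mean of 1.00, a minimum of 0.002 and a maximum of 1.998 years. None is at or below zero. The smallest value, for onset on 1 January and consent on 31 December, is about one day; it becomes zero if days are counted inclusively.

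**Sensitivity of the mean.** Onset is taken as spread evenly over the year, so E[v] = 0.5. The last column comes from 1,000,000 simulated patients per row, with true duration uniform from 12 weeks to 30 years.

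| Consent timing (assumed) | E[u] | Mean by formula | Simulated mean |
|---|---|---|---|
| Even over the year | 0.5 | 1 + 0.5 − 0.5 = 1.00 | 1.00 |
| All January to March | 0.125 | 1 + 0.5 − 0.125 = 1.375 | 1.375 |
| All October to December | 0.875 | 1 + 0.5 − 0.875 = 0.625 | 0.623 |
| All at the start of January | near 0 | near 1.5 | 1.496 |
| All at the end of December | near 1 | near 0.5 | 0.497 |

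Against completed whole years, the SAP value is 1 or 2 years too high, with a mean of 1.50 when consent is even over the year.

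**Examples (illustrative dates).**

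- Onset 1 July 2012, consent 1 July 2022: SAP 11, true 10.0.
- Onset 31 December 2012, consent 1 January 2022: SAP 11, true 9.0.
- Onset 15 October 2022, consent 15 January 2023: 92 days, so outside the 12-week exclusion (84 days) if Screening starts at consent. SAP 2, true 0.25.

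**Without the added year.** The error becomes v − u, between −1 and +1 year. Its mean is 0 when consent and onset are spread similarly over the year (simulated 0.00).

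**Where the variable goes.** Duration is not among the covariates (SAP 4.9.1.3), the primary model terms (4.9.2.1) or the sample-size inputs (4.12). The subgroup list (4.9.1.7) splits patients by diabetic status and HbA1c, not by duration.

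**The case against.** The best defence is that the rule is a disclosed convention. Counting both the first and the last calendar year avoids reporting 0 for a patient diagnosed in the year of consent, and a reader who knows the rule can subtract one. For some patients it is also closer to the truth: with onset in January and consent in November of the same year, true duration is about 0.8, and the SAP's 1 beats a plain difference of 0. This last point stands and belongs in the cost of the fix. The rest does not rescue the rule, because calendar years touched is a different quantity from the stated duration in years, and a table reader would not know to subtract.

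The mislabelled line is plainly a copy error. Its parent bullet is Type 2 and the formula refers only to the disease in question. A reader might infer that the Type 2 row will report Type 1 durations; that is unlikely in practice. What stands is that the text needs correcting before tables are programmed from it.

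A reader might also infer that the error misdescribes a main route into the trial, since Type 2 diabetes alone meets the increased-risk criterion in the group with TG from 150 to below 500 mg/dL. The documents do not support that weight. They give no proportion entering through diabetes, there are other routes in that group, and the severe hypertriglyceridemia group needs no diabetes. Eligibility does not use the derived duration. Nor can the rule be said to make recent disease look established, because no section sets a duration threshold for that.

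**Conclusion.** Both parts hold, as a minor correction. The rule overstates elapsed duration for essentially every patient, by more than 0 and less than 2 years, and this does not depend on any assumed distribution of dates. The mean of about 1 year does: it requires consent and onset to have the same average position in the calendar year. With onset spread evenly, extreme consent timing moves it to about 0.5 or 1.5. It would therefore be wrong to treat the excess over true duration as exactly one year for each patient.

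The Type 2 duration is undefined as written, although the intent is clear.

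The consequence stops at the targeted medical history table and listing. A reader might infer some effect on the efficacy conclusions; there is none, because no inferential analysis uses the variable. All arms share the rule, so comparison between arms is little affected.

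**What to change.** - In both duration lines of SAP 4.7, delete the added year, leaving consent year minus start year.
- If full onset dates are collected, (consent date − onset date)/365.25 has no systematic error. The documents do not show that they are, and the year-based rule suggests they may not be. If only some patients have full dates, state which rule applies to whom, because the summary would then mix two precisions.
- Change the label of the second line to Type 2.

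The cost is a few words and about one line of code. There is one small downside: with year-only data, a patient diagnosed in the calendar year of consent is reported as 0 years. A footnote, or display as <1 year, covers this. If the sponsor prefers to keep the present count, the row should be relabelled as calendar years counted inclusively, with the rule in a footnote.

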**Medication history:**

- Statins
  - Reason not on statins
- Any other lipid lowering therapy
  - Reason not on lipid lowering therapy

**Hematologic disorder history:**

- Bleeding diathesis or coagulopathy

**Pancreatitis history:**

- Acute pancreatitis or any symptoms suggestive of pancreatitis with hospitalization
- Acute pancreatitis or any symptoms suggestive of pancreatitis without hospitalization
- Known Chronic Pancreatitis

**Previous Treatment:**

- Previous treatment with volanesorsen
- Previous treatment with olezarsen

## 4.8 Prior and Concomitant Medication

Medication start and stop dates will be compared to the date/time of the first dose of study drug to allow medications to be classified as prior medication, and concomitant medication.

Any medication taken prior to the first dose of study drug will be classified as a prior medication, regardless of whether continued while on treatment or not. Any medication taken on or after the first dose of study drug will be classified as a concomitant medication.

Partial or missing medication start and/or stop date(s) will be imputed by the following imputation rules:

### **Missing or partial start date:**

- If year, month and day are all missing then assign the date of first dose of Study Drug
- If month and day are missing and year is:
  - earlier than the year of the first dose of Study Drug then assign December 31
  - otherwise, assign January 1
- If only day is missing, and month-year is:
  - earlier than the month-year of the first dose of Study Drug then assign the last day of the month
  - otherwise, assign the first day of the month

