### 5.1 Inclusion Criteria

1. Must have given written informed consent (signed and dated) and any authorizations required by local law and be able to comply with all study requirements
2. Aged  $\geq 18$  years at the time of informed consent
3. Fall into at least 1 of the following groups (a or b):
  - a. Hypertriglyceridemia with fasting TG  $\geq 150$  mg/dL (1.69 mmol/L) and  $< 500$  mg/dL (5.65 mmol/L) with either
    - Clinical diagnosis of ASCVD defined as documented coronary artery disease (CAD), cerebrovascular disease, or peripheral artery disease ([Appendix F](#)), or
    - At increased risk for ASCVD defined as:
      - Type 2 Diabetes mellitus, or
      - Two (2) or more of the following cardiovascular (CV) risk enhancing factors:
        - Men  $\geq 55$  years of age or women  $\geq 65$  years of age
        - Women with a history of preeclampsia, or premature menopause (before the age of 40 years)
        - Family history of premature ASCVD (before the age of 55 years for males, or before the age of 65 years for females)
        - Current tobacco use (5 cigarettes/day or more for at least 1 year)
        - Metabolic syndrome (see [Appendix F](#) for definition)

- Hypertension requiring antihypertensive treatment
- Chronic kidney disease stage 3 or (eGFR 30-59 mL/min/M)
- LDL-C  $\geq$  160 mg/dL
- LDL-C  $\geq$  100 mg/dL on therapy to lower LDL-C
- Elevated high-sensitivity C-reactive protein ( $\geq$  2.0 mg/L)
- Elevated lipoprotein (a) ( $\geq$  50 mg/dL or 125 nmol/L)
- Ankle brachial index  $<$  0.9 in asymptomatic patients
- Coronary artery calcium score  $\geq$  100

b. Severe hypertriglyceridemia with fasting TG  $\geq$  500 mg/dL (5.65 mmol/L)

**Note:** TG levels must meet inclusion criteria at both the Screening Run-In Visit and the Screening Qualification Visit. If the fasting TG is below the required level at a Visit, up to 2 additional tests may be performed with the average of the tests used to consider eligibility at that Visit.

4. Patients should be on standard of care (SOC) lipid-lowering medications per local guidelines ([Appendix E](#)). Lipid-lowering medications should be optimized and stabilized for at least 4 weeks prior to Screening to minimize changes in these medications during the study. Patients taking over-the-counter (OTC) omega-3 fatty acids should make every effort to remain on the same brand through the end of the study

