### **Missing or partial end date:**

Imputation will be performed for the end date only if the day or month is missing (i.e., year is present):

- If month and day are missing, then assign December 31
- If only day is missing, then assign the last day of the month

If the imputed start date is later than the imputed end date, then set the imputed start date to the imputed end date.

Prior and concomitant medications will be coded using the World Health Organization - Drug Dictionary Enhanced (WHO-DDE) and summarized by Anatomical Therapeutic Chemical (ATC) drug class, preferred term (PT) and by treatment group, total olezarsen treated and overall based on the Safety Set. Actual versions of WHO-DDE used will be stated in the clinical study report.

The number and percentage of patients in each of the following categories will also be summarized by treatment group, total olezarsen treated, and overall using the Safety Set:

- Not taking statins at baseline
  - Initiated statins after study drug administration
  - Taking statins at baseline
- Increased statin dose or switched to higher intensity after study drug administration

All prior and concomitant medications will be listed based on the Safety Set.

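### SAP 4.8 dates a medication with a wholly unknown start to the first dose, so a long-standing drug still in use is classed as concomitant but not prior; baseline lipid-therapy status needs a stated source.

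*Combined protocol and SAP*

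**What the plan says.** SAP 4.8 compares medication start and stop dates with the first dose "to allow medications to be classified as prior medication, and concomitant medication". The two classes are defined as follows:

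- Prior: "Any medication taken prior to the first dose of study drug will be classified as a prior medication, regardless of whether continued while on treatment".
- Concomitant: "Any medication taken on or after the first dose of study drug will be classified as a concomitant medication".

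A drug can belong to both. When the start date is wholly missing, the rule is: "If year, month and day are all missing then assign the date of first dose of Study Drug". Partial start dates have their own rules. A year or month before that of first dose goes to its last day; otherwise it goes to its first day. An imputed start later than the imputed end is moved back to that end.

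SAP 4.8 then lists a statin table covering use and non-use at baseline, with a category "Initiated statins after study drug administration". SAP 4.9.1.7 lists subgroups by "Baseline background therapies (lipid-modifying therapy versus none; statins versus no statins; Fibrates vs. no Fibrates". Neither place says how baseline use is derived. SAP 4.7 separately records, as targeted medication history, statins and any other lipid-lowering therapy, each with the reason if the patient is not on it. It has no separate fibrate item.

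Protocol 5.1, criterion 4, states: "Lipid-lowering medications should be optimized and stabilized for at least 4 weeks prior to Screening".

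**The concern.** An adverse event of unknown onset is dated to first dose so that it counts as treatment-emergent. SAP 4.10.2.3 calls its imputation rules conservative, and for events that is right. SAP 4.8 applies the same choice to medications without giving a reason, and there it works the other way. When not even the start year of an ongoing drug is known, long-standing use is the likelier explanation. For a lipid drug, criterion 4 makes that likelier still. Dating the start to first dose removes the record from prior medications, where it most plausibly belongs.

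What is certainly at stake is the accuracy of the prior-medication summary. What may be at stake, depending on an unstated derivation, is the statin table and the background-therapy subgroups of the TG endpoints. In a trial that asks for standard-of-care lipid therapy, the untreated subgroups may be small, and a few misplaced patients could then matter.

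**Working it through.** The SAP gives no figure to reproduce here, so the check is to apply the SAP 4.8 rules to test records. The first-dose date below, 15 September 2022, is chosen only for illustration. The rule moving the start back to the end date is read as covering any known end date.

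| Start recorded | Stop recorded | Start after imputation | Prior? | Concomitant? |
|---|---|---|---|---|
| nothing | ongoing | 15 Sep 2022 | no | yes |
| nothing | 1 Mar 2023 | 15 Sep 2022 | no | yes |
| nothing | Dec 2021 | 31 Dec 2021 (moved back to end) | yes | no |
| 2015 | ongoing | 31 Dec 2015 | yes | yes |
| 2022 | ongoing | 1 Jan 2022 | yes | yes |
| Aug 2022 | ongoing | 31 Aug 2022 | yes | yes |
| Sep 2022 | ongoing | 1 Sep 2022 | yes | yes |

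The first two rows come out the same with first-dose dates of 1 September 2022 and 1 January 2022. The partial-date rows change only at the edges: a drug dated to the month of first dose is not prior if dosing falls on the 1st, and one dated to the year of first dose is not prior if dosing falls on 1 January.

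Two results follow.

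1. For a long-standing drug, prior status is lost when even the start year is missing and the drug is still in use at first dose. Knowing only an earlier year is enough to keep it.
2. The rules pull in different directions. No date information gives not prior. Knowing only the year or month of first dose normally gives prior, even though the drug may have begun after dosing.

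Next, which outputs use the result:

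- **Prior-medication summary (SAP 4.8).** It depends directly on the classification, so each such record is wrongly omitted if the drug was in use before first dose.
- **Statin table (SAP 4.8).** It follows the date rules with no derivation of its own. The imputed dates are a natural source, but the text does not name them.
- **Background-therapy subgroups (SAP 4.9.1.7).** No source is stated. Targeted history could supply the statin and any-lipid-therapy splits. For fibrates it has no item, which leaves the medication records, where these date rules apply.
- **Primary analysis (SAP 4.9.2.1).** The ANCOVA contains treatment and log baseline TG only. The secondary models in SAP 4.9.3 add, where anything, the baseline TG stratum or the pancreatitis history. None uses background therapy.

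**The case against.** The strongest reply is that the documents tie the imputed dates to the prior and concomitant classes and to nothing else. A reader might infer that a long-standing statin or fibrate user with no start date necessarily lands in the untreated baseline subgroup and is reported as having started a statin on study. The text does not support that. Baseline status is nowhere linked to the prior flag or the imputed start. SAP 4.7 holds another record of statin and other lipid-lowering use. A start on the date of first dose is also not clearly after administration. This part of the reply stands, and the effect on the subgroups and statin table is conditional.

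A reader might also try to put a size on the contamination. Suppose 144 of 152 patients take some lipid drug, 8 take none, and a fraction q of users have no start date. The share of the untreated group that is really treated is 144q/(8 + 144q). That is 1.44/9.44 = 15% at q = 0.01 and 7.2/15.2 = 47% at q = 0.05. Every input is assumed, and the sum needs each affected patient to have all of their lipid drugs undated; one dated statin keeps a patient out of the untreated group. It cannot be offered as the size of the problem.

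Nor does criterion 4 show that a lipid drug dated to the month of first dose must be new. It says what should be the case, not what must be.

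Finally, such records may be few. Criterion 4 directs sites to the stability of lipid drugs before Screening, and protocol 12.4 plans data queries for omissions. In a blinded trial there is also no evident reason for a missing pre-dose start date to depend on treatment arm, so the error would blur a subgroup label rather than bias the comparison within it. All of this limits the consequence. None of it defends the rule, which still gives the less plausible answer for an ongoing drug.

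**Conclusion.** The rule as written misclassifies long-standing therapy: a drug with a wholly unknown start that is in use at first dose is recorded as concomitant and not prior. The prior-medication summary is wrong for each such record. That rests only on the SAP text and on the drug having in fact been taken before first dose, which criterion 4 makes likely for lipid drugs.

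Misplacement in the statin table and the background-therapy subgroups is a conditional risk. It arises if baseline use is programmed as a start before first dose, and would not arise if use on Day 1 counted as baseline. The fibrate subgroup is the most exposed, because targeted history cannot settle it.

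The number of affected records is not given, so no size can be stated. The primary and confirmatory secondary analyses are not affected. The exposure is confined to descriptive medication tables and to subgroup analyses meant to assess consistency. It is a modest point, but cheap to correct.

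**What to change.** In SAP 4.8, classify a medication with a wholly missing start date as prior, and also as concomitant if it was not stopped before first dose, unless the stop date or the eCRF shows that it began on or after first dose.

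In SAP 4.8 and 4.9.1.7, state the source of baseline status:

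- **Statins and any lipid-modifying therapy:** the targeted medication history of SAP 4.7. Appendix A of the protocol schedules medical history at run-in, so a check against medication records for a change before Day 1 is sensible.
- **Fibrates:** medication records showing use at first dose, with a wholly missing start counted as baseline use.

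The cost is a few sentences and one derivation change, with no new data and no effect on the confirmatory tests. SAP Section 1 allows updates to the analyses. If the database is already locked, the same section provides for documenting the change in the clinical study report.
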